4.4.6 Cardiac Evaluation

All subjects will undergo a baseline ECG prior to enrollment. An ECG will also be performed on Cycle 1 Day 15. ECGs will be reviewed by the investigator and confirmed by a cardiologist. Standard triplicate 12-Lead ECG (2 minutes apart) is recommended in all visits; the combined QTcF values from these triplicate ECGs will be averaged to provide a single value for each time point. For patients with QTcF ≥ 481 ms at any time, interrupt study treatment and follow the procedures described in Table 9. If treatment is resumed, repeat ECGs 7 days and 14 days after dose resumption (and then as clinically indicated). During subsequent cycles, a predose ECG will be performed for every cycle starting at cycle 6, and predose and 2-4 postdose starting at cycle 9 and every 3rd cycle thereafter.

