4.4 Detailed Patient Assessments

Subject assessments (physical examinations, vital signs, performance status, chemistry, hematology, medication review, and adverse event evaluations) will be conducted at screening, Cycle 1 Day 1, every 2 weeks thereafter until the first response assessment at 8 weeks, and then every 4 weeks thereafter. Study visits and the on-treatment tumor biopsy may be performed 3 days before or after the scheduled date due to unforeseen or unavoidable circumstances, and attempts should be made to schedule visits to line up with the start of a new cycle (within the constraints of the above parameters). Study drugs will be dispensed at the last visit prior to the start of the next 28 day cycle. The radiologic first response assessment at 8 weeks, and subsequent radiologic response assessments every 8 weeks thereafter, may be performed up to 7 days before or after the scheduled date due to unforeseen or unavoidable circumstances. Details are provided in Table 5, and a checklist highlighting the important events for screening through the completion of the trial is provided below, as Table 6.

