4.4.12 Protocol Deviations

The investigator should not implement any deviation from the protocol without prior review and agreement by the Sponsor and in accordance with the IRB and local regulations, except when necessary to eliminate an immediate hazard to study subjects.

Table 7. Study Activities

	Screening Visit	Cycle 1, Day 1	Cycle 1, Day 15	Every 2 Weeks thereafter until 1st Response Assessment	Cycle 2, Day 1	First Response Assessment (at 8 Weeks)	Every 4 Weeks after 1st Response Assessment	Every 8 Weeks after 1st Response	Off Study	Follow-up Assessments ^g
Informed consent	X									
Demographics	X									
Medical history	X	X	X	X	X	X	X	X	X	
Concurrent meds	X	X	X	X	X	X	X	X	X	
β-hCG	X ^a	X ^a								
Vital signs	X	X	X	X	X	X	X	X	X	
Height	X									
Weight	X	X	X	X	X	X	X	X	X	
History and physical	X	X	X	X	X	X	X	X	X	
Performance status	X	X	X	X	X	X	X	X	X	
Adverse event evaluation	X	X	X	X	X	X	X	X	X	
CBC w/ diff.	X	X	X	X	X	X	X	X	X	
Serum chemistry ^b	X	X	X	X	X	X	X	X	X	
Tumor markers ^c	X	X			X	X		X	X	
Radiologic evaluation and tumor measurements ^d	X					X		X	X ^h	
PT/PTT	X ^e		X ^e							
Tumor biopsy	X		X							
Research serum sample for ctDNA	X	X					X		X ⁱ	
Electrocardiogram (EKG) ^f	X									
Dispense study medications		X			X	X	X	X		
Survival		X	X	X	X	X	X	X	X	X

^aUrine or serum pregnancy test (women of childbearing potential)
^bAlbumin, alkaline phos., total bili., bicarbonate, BUN, calcium, chloride, creatinine, glucose, potassium, total protein, AST, ALT, sodium, phosphorus, magnesium
^cTumor marker (CA 19-9 or CEA)
^dScreening scans should be within 3 weeks of starting treatment
^eFor biopsy
^fElectrocardiograms should be done in triplicate, reviewed by the investigator, and confirmed by cardiology
^gUp to 24 months
^hUnless performed within 4 weeks of the off study date
ⁱOptional

Table 8. Study Activities Checklist

Screening

Subject assessment	_____
Eligibility criteria met	_____
Informed consent	_____
Demographics	_____
Medical History	_____
Concurrent medications	_____
ECG	_____
Pregnancy test (if appropriate)	_____
Vital signs	_____
Height	_____
Weight	_____
History and physical	_____
Performance status	_____
CBC with differential	_____
Serum chemistries	_____
PT/PTT/INR	_____
Radiologic Assessment	_____
Tumor amenable to biopsy	_____
Pre-treatment biopsy	_____

Cycle 1, Day 1

Subject assessment	_____
Concurrent medications	_____
Pregnancy test (if appropriate)	_____
Vital signs	_____
Weight	_____
History and physical	_____

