5.2 Packaging and Labeling of LEE011 and Everolimus

Film coated tablets of LEE011 will be packaged in bottles containing 200 mg and 50 mg tablets (75 tablets per bottle), and patients will be supplied with sufficient tablets for one cycle, plus enough for one extra day (see Table 7).

Table 9. Dispensation of LEE011 by Dose Level

Dose Level	Dose	200 mg Tablets Dispensed	50 mg Tablets Dispensed
2	300 mg	22	44
1	250 mg	22	22
-1	200 mg	22	0
-2	150 mg	0	66

Everolimus will be packaged in bottles containing 2.5 mg tablets with sufficient tablets in the bottle for once cycle, plus enough for one extra day (29 pills). Each bottle will be labeled with an open-label white single panel or booklet label that will include, but is not limited to, the following information:

- 1) Protocol number
- 2) Drug identification
- 3) Number of capsules
- 4) Storage conditions
- 5) Dosing instructions
- 6) Blank spaces to write the subject's identification number, initials and date dispensed

Each bottle label must remain affixed to the bottle.

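### Table 7 omits the Cycle 1 Day 15 ECG that 4.4.6 and Table 8 require, and the Appendix C registration checklist is looser than Sections 3.2 and 3.3

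*Combined protocol and SAP*

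**What the plan says.** **ECG schedule.** Section 4.4.6 requires a baseline ECG and then states: "An ECG will also be performed on Cycle 1 Day 15". For later cycles, "a predose ECG will be performed for every cycle starting at cycle 6, and predose and 2-4 postdose starting at cycle 9" and every third cycle after that. It adds: "Standard triplicate 12-Lead ECG (2 minutes apart) is recommended in all visits". Table 8 has an ECG line at Screening, Cycle 1 Day 15 and Cycle 2 Day 1. In Table 7 the row beginning "Electrocardiogram (EKG" has one mark, under Screening; its footnote covers triplicate recording and review and names no visit. Section 4.4 allows that "Study visits and the on-treatment tumor biopsy may be performed 3 days before or after the scheduled date".

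**What the ECG feeds.** Under 6.7.1.1 and Table 10, QTc of 501 ms or more on at least two separate ECGs is a DLT if it occurs in the first 4 weeks and is judged related to treatment. For QTcF of 481 ms or more, 4.4.6 tells sites to "interrupt study treatment and follow the procedures described in Table 9". Table 9 is headed "Dispensation of LEE011 by Dose Level"; the QT rules are in Table 11.

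**Eligibility.** Section 3.2 item 12 sets PTT at no more than 1.5 x ULN and INR at no more than 1.5, with an INR exception for anticoagulated patients. Appendix C, which research staff complete before registration, sets PT and PTT at no more than 2 x ULN and INR below 2, with the same exception. Section 3.3 exclusion 1 bars patients with earlier exposure to CDK or mTOR inhibitors, or who are intolerant of or ineligible for them. Appendix C has no such item.

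**The concern.** Table 7 and Appendix C are the pages a site is likely to work from day to day, and each is laxer than the section it summarises.

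On the ECG, symptomatic cardiac events have their own DLT row, so what is exposed is symptom-free QTc prolongation, which only an ECG can show. The second qualifying ECG is normally the repeat that Table 11 orders after a first high reading, so missing the Day 15 tracing can lose both. The recommended phase II dose depends on whether a dose level has 0 to 1 or at least 2 DLTs in 6 patients. A level with 2 true DLTs, one of them an undetected QTc event, would be recorded as 2 - 1 = 1 in 6 and accepted. The same tracing also triggers the treatment hold at 481 ms, so it matters in Phase II as well.

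On eligibility, the form can pass a patient whom the protocol excludes. Coagulation tests are in the schedule for the biopsies, two of which are mandatory unless judged unduly risky.

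**Working it through.** No formula or stated figure applies. The check sets the sources side by side and works out which visits fall in the DLT window.

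**Explicit ECG visits**

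| Source | Baseline/Screening | C1D15 | C2D1 | Later cycles |
|---|---|---|---|---|
| 4.4.6 | yes | yes | not named | from cycle 6; from cycle 9 |
| Table 8 | yes | yes | yes | none |
| Table 7 | yes | no | no | none |

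**Visit days against the DLT window** (Cycle 1 Day 1 is day 1, cycles last 28 days, the window is days 1 to 28)

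- C1D15: 15 - 3 = 12 to 15 + 3 = 18, always inside.
- C2D1: 29 - 3 = 26 to 29 + 3 = 32, inside only if held on day 26, 27 or 28.

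Scheduled on-treatment ECGs in the window are therefore 0 by Table 7 and 1 by Table 8 (2 if C2D1 is held early). By 4.4.6 there is 1, if the all-visits sentence concerns only the triplicate format. If it means an ECG at every visit, there would be more, but the sentence is a recommendation and does not settle which is meant.

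**Could Table 7 have been damaged in conversion?** Its ctDNA row does not match 4.4.4, so marks may have moved between columns. A move cannot explain the ECG row, which has 1 mark where 4.4.6 needs at least 2. Only a lost mark could, and the PT/PTT and biopsy rows kept their C1D15 marks. A lost mark is unlikely but not excluded.

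**Eligibility limits**

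| Item | 3.2 / 3.3 | Appendix C | Passes the form, fails the protocol |
|---|---|---|---|
| PTT | at most 1.5 x ULN | at most 2 x ULN | above 1.5, up to 2 x ULN |
| INR, no anticoagulant | at most 1.5 | below 2 | above 1.5, below 2 |
| PT | no limit | at most 2 x ULN | none; the form is stricter here |
| Exclusion 1 | excluded | no line | e.g. CDK or mTOR inhibitor more than 3 weeks earlier |

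The form's 3-week wash-out line catches only recent treatment, hence the last row. Inclusion 16 (able to swallow tablets whole) and the contraception commitment in inclusion 15 also have no line.

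**Table number.** The citation of Table 9 in 4.4.6 is one of 14 table citations that are two too low. They are in 3.2 item 5, 3.3 item 14, 3.4.5, 3.4.6, the screening text of 4.2 (two), 4.2.1.8, 4.4 (two), 4.4.4, 4.4.6, 5.2 and Appendix C (two): 1+1+1+1+2+1+2+1+1+1+2 = 14.

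**The case against.** The strongest reply is that the Day 15 ECG is already stated twice, in the governing section and in the visit checklist. Section 4.4 sends sites to both tables, so harm needs a site that uses Table 7 alone. That is fair as to likelihood, but it does not make Table 7 right.

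On eligibility, exclusion 1 is also the first key exclusion in the synopsis, Table 8 has a line for eligibility being met, central reviewers must confirm eligibility before treatment (4.4.11.2), and Appendix D records prior therapies. These lower the risk but leave two different coagulation limits in force. The biopsy link is also weaker than it looks: the first biopsy follows consent as soon as possible, the form is due only before registration, and 4.3.1 has biopsies done under the radiology department's standard protocol.

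A reader might infer more than the documents support:

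- **That Cycle 2 Day 1 is a second missed ECG.** The same Table 8 block lists PT/PTT/INR, which neither 4.4.4 nor Table 7 schedules there. The block may have been carried over from Day 15, so its ECG line is not settled intent.
- **That Table 8 conflicts with 4.4.6 on later cycles.** Section 4.4 describes it as "a checklist highlighting the important events for screening through the completion of the trial is provided below", so silence there is not a contradiction.
- **That inclusion 15 and exclusion 7 are wholly absent from Appendix C.** The pregnancy-test part of inclusion 15 is there, and exclusion 7 overlaps the line on understanding and complying.
- **That the wrong table number is a QT fault.** It is clerical and systematic, the same sentence already orders treatment to stop, and 6.7.1.2 cites Table 11 correctly.

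**Conclusion.** The point holds for three items: the missing Day 15 mark in Table 7, the looser coagulation limits in Appendix C, and the missing line for exclusion 1. These are internal inconsistencies in operating documents and should be corrected.

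Their size is 0 scheduled on-treatment ECGs in the DLT window by Table 7, against at least 1 by 4.4.6 and Table 8, and eligibility bands of 1.5 to 2 x ULN for PTT and 1.5 to 2 for INR off anticoagulants. The documents give no frequency for silent QTc prolongation, for values in those bands or for prior CDK or mTOR treatment, which is probably uncommon here. It would therefore be wrong to infer a numerical effect on DLT counts, the Simon two-stage design or power. The ECG part assumes that the Table 7 row is printed as the sponsor wrote it.

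**What to change.** - **Table 7:** mark the ECG at Cycle 1 Day 15, and add a footnote for the 4.4.6 ECGs from cycle 6 and from cycle 9.
- **Section 4.4.6:** change the reference from Table 9 to Table 11, ideally while correcting the other 13 table numbers.
- **Appendix C limits:** set PTT to at most 1.5 x ULN and INR to at most 1.5 with the anticoagulation exception. Drop the separate PT limit, since 3.2 sets none.
- **Appendix C items:** add exclusion 1, the pregnancy-avoidance commitment of inclusion 15, and inclusion 16.
- **Query to the sponsor:** is the Cycle 2 Day 1 ECG in Table 8 intended? Add it to Table 7 or 4.4.6 only if so. The same query can settle whether the all-visits sentence in 4.4.6 means an ECG at every visit or only the triplicate format.

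The cost is edits to one table, one section and one form. Apart from whatever the query settles, no procedure or criterion is added beyond those already in 4.4.6, 3.2 and 3.3.

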4.4.7 Adverse Event Evaluation

The Principal Investigator or sub-investigators will assess adverse events, laboratory data and vital signs throughout the study. Adverse events will be assessed by NCI CTCAE Version 4.03. http://evs.nci.nih.gov/ftp1/CTCAE/CTCAE_4.03_2010-06-14_QuickReference_8.5x11.pdf The investigators will monitor each subject for clinical and laboratory evidence of adverse events on a routine basis throughout the study. The investigator will assess and record any adverse event in detail including the date of onset, event diagnosis (if known) or sign/symptom, severity, time course, duration and outcome, relationship of the adverse event to study drug, and any action(s) taken. For serious adverse events not considered "probably related" to study drug, the investigator will provide an "Other" cause of the event. For adverse events to be considered intermittent, the events must be of similar nature and severity. Adverse events, whether in response to a query, observed by site personnel, or reported spontaneously by the subject will be recorded. All adverse events will be followed to a satisfactory conclusion.

4.4.8 Imaging and Response Evaluation

Patients will undergo a baseline tumor evaluation with imaging studies within 3 weeks prior to Cycle 1 Day 1. Imaging studies should include a diagnostic CT scan of the chest, abdomen, and pelvis with PO and IV contrast (unless medically contraindicated). If a patient has an allergy to IV contrast, appropriate pre-medication can be given to prevent a contrast reaction. Patients may undergo other modalities such as an MRI instead of a CT scan at the treating physician's discretion if appropriate (such as severe allergy to CT contrast, extremity tumors, bone metastases requiring bone scans, etc.).

Response evaluation will occur every 8 weeks (regardless of treatment cycle) and at the final visit, if not performed within the last 4 weeks. Tumor response and/or disease progression will be assessed by the modality(ies) used prior to treatment. Patients will continue to remain on study as long as there is no evidence of PD and the therapy is adequately tolerated.

4.4.9 Removal of Subjects from Therapy or Assessment

4.4.9.1 Reasons for Removal of Subjects from Therapy or Assessment

Each subject has the right to withdraw from study treatment at any time. In addition, the investigator may discontinue a subject from the study treatment at any time for any reason if the investigator considers it necessary, including the occurrence of an adverse event or noncompliance with the protocol. Each subject will be withdrawn from the study if any of the following occur:

- 1) The subject experiences either clinical or radiographic progressive disease.
- 2) The subject requires radiotherapy or alternate antineoplastic agents during the study period.
- 3) The investigator believes it is in the best interest of the subject.
- 4) Clinically significant deterioration of the subject's medical status as determined by the investigator.
- 5) Subject becomes pregnant or begins breastfeeding during the treatment portion of the study.
- 6) The subject or subject's legally acceptable representative decides to withdraw consent for any reason.
- 7) Any other medical reason that the study investigator deems appropriate.

4.4.9.2 Discontinuation of Individual Subjects

When a subject discontinuation from the study (without reaching a protocol-defined endpoint) is planned, the investigator will notify the PI as soon as possible (provided, in each case, subject care and safety are not compromised). When a subject discontinues the study, a final visit will be conducted (preferably prior to the initiation of another anticancer therapy). However, these procedures should not interfere with the initiation of any new treatments or therapeutic modalities that the investigator feels are necessary to treat the subject's condition. Following discontinuation of the study drug, the subject will be treated in accordance with the investigator's best clinical judgment. At the final visit, the reason(s) for the discontinuation from the study will be recorded and a physical examination, body weight, vital signs measurement, laboratory analyses, performance status, tumor assessment, collection of unused study drug and an assessment of adverse events will be performed as soon as possible after discontinuation from the study. All subjects will have one final visit, which does not need to be performed for subjects who have had a visit greater than 30 days after discontinuation of the study drugs. If a subject is discontinued from the study with an ongoing adverse event or an unresolved clinically significant laboratory result, personnel will attempt to provide follow-up until a satisfactory clinical resolution of the laboratory result or adverse event is achieved. In the event that a positive result is obtained on a pregnancy test for a subject during the study, the administration of study drug to that subject must be discontinued immediately.

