4.4.10 Longitudinal Outcomes Assessment

Subsequent therapies will be administered at the discretion of the treating physician. Patients will be followed after progression until death (or up to 24 months) to assess overall survival. Information pertaining to survival and post-treatment therapy will be collected approximately every 12 weeks (Month 3, 6, 9, 12, 15 and 18) beginning after the final visit, for a period up to 24 months.

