Research serum sample for ctDNA _____
Tumor biopsy (optional) _____

Follow-up assessment(s)

Subject assessment (may be done via phone) _____
Vital status data collection _____

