6.4 Adverse Event Collection Period

All adverse events reported from the time of study drug administration until 30 days following discontinuation of study drug administration have elapsed will be collected, whether elicited or spontaneously reported by the subject. In addition, serious adverse events will be collected from the time the subject signed the study-specific informed consent.

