9.5.2.3 Adverse Events

Analyses of adverse events (and serious adverse events) will include only "treatment-emergent" events, *i.e.*, those that have an onset on or after the day of the first dose of study drug. Analyses will not include those that have an onset greater than 30 days after the last dose of study drug. Treatment emergent adverse events will be summarized by system organ class and preferred term according to the MedDRA adverse event coding dictionary. The percentage of subjects experiencing an adverse event at a given severity, NCI CTCAE toxicity grade, and relationship to study drug will be provided.

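### Adverse events are reported to 30 days after the last dose, but no enquiry is scheduled at or near day 30, so new non-fatal events after the final visit are captured only passively

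*Combined protocol and SAP*

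**What the plan says.** **The window.** Section 6.4 says that adverse events reported "until 30 days following discontinuation of study drug administration have elapsed will be collected, whether elicited or spontaneously reported by the subject". Section 9.5.2.3 sets the same limit for analysis: "Analyses will not include those that have an onset greater than 30 days after the last dose of study drug". Section 9.5.2.4 also uses a 30-day cut for off-treatment deaths.

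**The last scheduled enquiry.** Section 4.4.9.2 provides one final visit, preferably before any new anticancer therapy, at which "an assessment of adverse events will be performed as soon as possible after discontinuation from the study". It sets no minimum day after the last dose. It then waives the visit, which "does not need to be performed for subjects who have had a visit greater than 30 days after discontinuation of the study drugs".

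**Later contacts.** Section 4.4.10 states: "Information pertaining to survival and post-treatment therapy will be collected approximately every 12 weeks". These contacts begin after the final visit, the first at Month 3. In Table 7 the adverse-event row ends at Off Study, and the follow-up column is marked for survival only. The follow-up block of Table 8 has a subject-assessment line that may be completed by phone and a vital-status line. It has no separate adverse-event line, although the off-study block and every on-treatment block have one.

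**The concern.** The window and the schedule do not match. The plan reports safety as covering treatment plus 30 days, but active enquiry stops at the final visit, and nothing requires that visit to fall at or near day 30. Where it falls earlier, the remaining days rely on passive capture, which is weaker than the direct questioning used at every treatment visit. A new infection, pneumonitis or cytopenia that starts in those days and is not fatal could be missed.

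What is at stake is the safety and tolerability objective (Section 2.2.4), with its count of grade 3 and 4 toxicities (Section 2.5.4), and the treatment-emergent tables of Section 9.5.2.3. Because the trial is single-arm, those rates will be read as absolute figures, and missed events would bias them downwards.

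**Working it through.** The plan states no figure on this point, so there is none to reproduce. The check is one of timing.

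**Inputs**
- Window: W = 30 days after the last dose (Sections 6.4 and 9.5.2.3).
- Day of the final visit, counted from the last dose: t. The protocol gives no value, so a range is shown as an assumption.
- Interval from the final visit to the next contact: about 12 weeks = 84 days (Section 4.4.10).
- Longest retreatment delay while a toxicity resolves: 3 weeks = 21 days (Section 6.7.1.2). A patient who leaves the study after such a hold would have t of about 21.

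**Formulas**
- Days of the window after the last scheduled enquiry = 30 − t; share = (30 − t)/30.
- Next contact = day t + 84, which is t + 84 − 30 = t + 54 days after the window closes.

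**Results**

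| Final visit (day t) | Days left | Share of window | Next contact (about day) |
|---|---|---|---|
| 0 | 30 | 100% | 84 |
| 3 | 27 | 90% | 87 |
| 7 | 23 | 77% | 91 |
| 14 | 16 | 53% | 98 |
| 15 | 15 | 50% | 99 |
| 21 | 9 | 30% | 105 |
| 28 | 2 | 7% | 112 |
| 30 | 0 | 0% | 114 |

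More than half of the window is left only if the final visit falls before day 15. For any visit up to day 30, the next contact comes 54 to 84 days after the window has closed.

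**What is still captured between the final visit and day 30**
- Events open at discontinuation: followed to resolution (Section 4.4.9.2).
- Deaths: found through survival follow-up and summarised (Sections 4.4.10 and 9.5.2.4).
- Serious events that reach the investigator after drug is stopped and are judged at least possibly related: reported (Section 6.5).
- Events that staff observe or patients report: recorded (Sections 4.4.7, 6.1 and 6.4).

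What remains without a scheduled enquiry is the new, non-fatal event.

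**Scale of a single miss.** One patient missed among 26 changes a reported rate by 1/26 = 3.8 percentage points; among 44 (the planned maximum), by 1/44 = 2.3 points. This shows sensitivity only. The documents give no basis for estimating how many events would be missed.

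**The case against.** The strongest reply is that Section 4.4.9.2 ties the final visit to leaving the study, not to the last dose. A patient on a dose hold stays on study and is still seen every 2 or 4 weeks (Section 4.4). After a 3-week hold only about 9 of the 30 days remain. Some hepatic rows of Table 11 take a patient off study only after recovery has exceeded 21 or 28 days, which leaves little or nothing. The waiver also suggests that the authors had a visit after day 30 in mind. And Section 4.4 includes adverse-event evaluation in its definition of subject assessments, so the phone line in Table 8 might be read to cover it.

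The first argument stands, and it limits the size of the gap. The other two do not close it. The waiver excuses the final visit if a later one has already happened; it requires none. Section 4.4 schedules its subject assessments at screening and during treatment, Table 7 marks survival alone in follow-up, and a first call at about 12 weeks would be late recall.

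Three stronger readings are tempting, and the documents do not support them:
- A reader might infer that most of the window is unassessed in every patient. That depends on a final visit before day 15, and patients who die on treatment have no such window.
- A reader might infer that later events surface only if the patient volunteers them. Sections 4.4.7, 6.1 and 6.5 allow other routes.
- A reader might infer that the gap falls mainly on those who stop for toxicity. Those who stop after a failed hold have the smallest gap, and their open toxicities are followed. The inference fits immediate discontinuation better, whether for toxicity or for progression.

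**Conclusion.** The point holds in a limited form. The plan reports adverse events to day 30 after the last dose but schedules no enquiry at or near that day. New non-fatal events that start after the final visit are therefore captured passively. The uncovered share ranges from 90% of the window (visit on day 3) to 7% (day 28), and it is zero if the visit falls on or after day 30. These shares rest entirely on the assumed day of the visit.

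The likely effect is some under-counting in the grade 3-4 and treatment-emergent summaries, of an amount that the documents do not allow one to estimate. The 8-week primary endpoint is not affected, nor is the choice of the Phase II dose, which rests on toxicities in the first 4 weeks of therapy (Section 6.7.1.1). No decision rule uses post-treatment events. The change is worth making because it is cheap and concerns a stated secondary objective; it does not threaten the trial's main conclusions.

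**What to change.** 1. In Section 4.4.9.2 and Table 7, with a matching line in Table 8, add one enquiry about adverse and serious adverse events at or just after day 30 from the last dose. Existing staff can make it by phone. It is unnecessary where the final visit itself falls on or after day 30. With it, the part of the window without a scheduled enquiry falls to 0 of 30 days, whatever the day of the final visit.
2. Reconcile the prompt timing and the waiver in Section 4.4.9.2 with each other and with the 30-day window in Sections 6.4 and 9.5.2.3. State whether the final visit is counted from leaving the study or from the last dose.
3. As a weaker fallback, add a question on events with onset within 30 days of the last dose to the first follow-up contact. It would rely on recall at least 54 days after the window closes.

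The cost is one short call per patient, with no new clinic visit and no change to treatment.
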